4.3 Scientific Rationale for Study Design

This study uses a double-blind design in order to avoid subjective influences in the study conduct and results evaluation. Random assignment is used to ensure balancing of external influences between the study arms.

The subject population and endpoint (BORR) have been chosen to provide an appropriate sensitivity to eventual differences in efficacy and safety of the DRL_RI and the reference product. The LTB-FL setting allows treatment with rituximab as a single agent, which maximises the sensitivity to differences in efficacy and safety between DRL_RI and the reference product due to the lack of interference by the effects of the concomitant therapies. The use of BORR as an endpoint also maximises sensitivity to differences in a reasonable time in this population, where the time to tumour growth is prolonged.

The current standard of care in advanced FL is rituximab in combination with chemotherapy. The indication for this study, anatomically defined, LTB, CD-20 positive FL, is a slow growing malignancy and rituximab monotherapy is an acceptable treatment option according to various treatment guidelines.^{3,4} The goal of treatment with rituximab monotherapy in LTB-FL is to relieve disease symptoms, to delay the time to treatments more difficult to tolerate such as chemotherapy, and to relieve anxiety related to disease.

Low tumour burden will be assessed according to the GELF based criteria.^{9,16}A serum LDH level within normal limits will be required for enrolment as LDH is an important prognostic factor in FL.

4.4 Justification for Dose

The 375 mg/m^2 of BSA is the dose of the RMP in clinical use for the treatment of follicular lymphoma. Thus, the same dose is maintained in order to allow a comparative evaluation of DRL_RI safety and efficacy with those of the reference product at the doses in current clinical use.

4.5 End of Study Definition

Subjects who complete the study or subjects who discontinue from the study early will attend an EOS/ET Visit. Subjects experiencing disease progression will discontinue study drug and attend the ET Visit, which is to be scheduled 8 weeks after the last dose of study drug administration. These subjects will then be contacted by telephone for information on survival, AEs, and concomitant medications (Section 4.5.1) every 8 weeks, for a total observation period of 52 weeks (Section 4.5.1). Subjects discontinued from study drug due to a reason other than disease progression will also attend the ET Visit scheduled 8 weeks after the last dose of study drug, and then will continue to attend scheduled tumour assessments (at which AE and concomitant medication information will also be collected) up to disease progression or Week 52, whichever occurs first, as described in Section 4.1.1.

End of Study/Early Termination assessments are as follows:

- 1. Clinical assessments will include the following: Physical examination (including weight), vital signs measurement (blood pressure, heart rate, respiration rate, and oral, axillary, or tympanic body temperature).
- 2. Serum pregnancy test (human chorionic gonadotropin [hCG]) for women of childbearing potential. Female subjects with documented history of hysterectomy, bilateral oophorectomy, medically confirmed ovarian failure, or screening follicle stimulating hormone (FSH) test demonstrating post-menopausal status are exempted from pregnancy testing.
- 3. ECOG performance status assessments.
- 4. Clinical laboratory tests: Blood and urine samples will be taken for haematology, coagulation, biochemistry, and urinalysis.
- 5. Serum LDH and β -2 microglobulin evaluation.
- 6. 12-lead ECG (local ECG equipment with ECG to be read locally by a medically qualified and experienced ECG reader at the study site).
- 7. Viral disease screening at the EOS Visit.
- 8. Tumour assessments (using a computed tomography [CT] scan and, where available according to study site standard of care, a fluorine-18-fluorodeoxyglucose positron emission tomography [[¹⁸F] FDG-PET] or PET-CT scan) based on central radiology review in accordance with the response criteria for malignant lymphoma.¹³
- 9. Samples for BAb and NAb will be obtained.

- 10. A pharmacodynamic sample will be obtained only in the subjects undergoing PK and pharmacodynamic assessments.
- 11. Bone marrow biopsies are required for any subject who has a response of CR at an evaluation point and either had a bone marrow examination positive for FL at Screening or shows new abnormalities in the peripheral blood counts or blood smear that clinically indicates a bone marrow evaluation is required.
- 12. Assess AEs.
- 13. Review concomitant medications.
- 14. COVID-19 questionnaire.

4.5.1 Telephone Assessments for Survival Follow-up

The procedures will include the following:

- 1. Check survival status.
- 2. Record AEs and concomitant medications.

4.5.2 Early Termination of Study

This study may be terminated prematurely at any time by DRL for medical, operational or ethical reasons at individual or all study sites.

If the study is prematurely terminated or discontinued, the Sponsor/designee will promptly notify the Investigator, institutions and all competent regulatory authorities in writing outlining the reasons for the termination. The Investigator or Sponsor/designee will promptly inform the Independent Ethics Committee (IEC)/Institutional Review Board (IRB). After notification, the Investigator must contact all participating subjects and the hospital pharmacies (if applicable) within a reasonable time period and inform them of the premature termination/discontinuation of the study.

As directed by the Sponsor/designee, all study materials, except documents needed for archiving requirements, will be collected and all eCRFs completed to the greatest extent possible. The study monitor will ensure that any outstanding data clarification issues and queries are resolved, and that all study records at the study site are complete.

4.5.3 Definition of End of Study and Primary Completion Date

End of Study is defined as the time at which all subjects enrolled in the study have been followed for 52 weeks unless lost to follow-up or the subject has died. The EOS is achieved at last subject last visit and when data from those visits have been reviewed by the Investigator or designee.

Primary Completion Date is defined as the date that the final subject was examined or received an intervention for the purposes of final collection of data for the primary outcome, whether the clinical study concluded according to the pre-specified protocol or was terminated. For the purposes of analysis, the study will be unblinded to specified Sponsor/designee members (but not investigators or subjects) once all subjects have reached the primary endpoint through the end of Week 28 (or earlier termination of study drug), and the database is locked.

For all those persons who will have access to the interim analysis unblinded data and results, will sign a confidentiality agreement in order to maintain study blind until the general unblinding happens after the final database lock.

5 Study Population

5.1 Inclusion Criteria

A subject will be eligible for enrolment in the study if he/she meets all of the following criteria:

- 1. Signed written informed consent.
- 2. Male or female subjects aged ≥ 18 years of age.
- 3. Histologically confirmed, Grade 1-3a, previously untreated, CD20-positive, LTB-FL as per GELF based criteria. Subjects must have sufficient tissue samples available for the central pathology review (Section 8.1.1), and a centrally -confirmed diagnosis prior to being randomised. Should a subject be eligible as per the central imaging review but not as per the Study Centre Review the subject will be considered eligible if confirmed both by the Investigator and the Medical Monitor (MM). For any other disagreement in eligibility the subject will be considered ineligible.
- 4. Ann Arbor Stage II to IV (Section 10.1.14).
- 5. ECOG status of 0 to 1.
- 6. Low tumour burden follicular lymphoma defined as:
 - As per central radiological assessment, nodal or extranodal mass involvement with diameter measuring <7 cm

- As per central radiological assessment, involvement of ≤3 nodal sites with diameter measuring >3 cm
- Absence of systemic symptoms or B-symptoms* (asymptomatic).

*B-symptoms defined as weight loss >10% within last 6 months, recurrent or continuous night sweats, intermittent or continuous fever recorded as axillary or oral temperature >38°C for at least 3 days

- As per central radiological assessment, absence of splenomegaly (defined as spleen size higher than 16 cm by CT scan)
- Absence of risk of vital organ compression based on clinical finding
- Absence of leukemic phase (leukemic phase defined as a count >5,000/µL of circulating tumour cells)
- Absence of clinically significant cytopenias (defined as a platelet count of <100,000/µL, haemoglobin <10 g/dL, or absolute neutrophil count <1,500/µL)
- Absence of clinically significant serous effusion based on clinical examination and CT scan
- Serum LDH not higher than the upper limit of normal (ULN) by local laboratory.
- 7. Subject has at least 1 measurable tumour mass in 2 dimensions as per central radiological assessment, and the mass must be:
 - Nodal lesion >15 mm in the longest dimension; or
 - Nodal lesion >10 mm to ≤15 mm in the longest dimension and >10 mm in the shortest dimension; or
 - Extranodal lesion with both long and short dimensions ≥ 10 mm.
- 8. Creatinine clearance \geq 45 mL/min as calculated by Cockcroft-Gault method.
- 9. Aspartate transaminase (AST), alanine transaminase (ALT), alkaline phosphatase (ALP) values $\leq 3 \times$ ULN, total or conjugated bilirubin values $\leq 1.5 \times$ ULN.
- 10. Life expectancy \geq 3 months.
- 11. Able to comply with the study protocol.

12. If female subject, then subject should be non-pregnant, non-lactating. Adequate contraception or post-menopausal/non-childbearing status (e.g., women with cessation of menstruation for ≤ 2 years, peri-menopausal women with inconclusive menopausal evidences based on clinical assessment and medical history). Women of childbearing potential must practice effective birth control for the duration of the study and for 12 months after the last study drug dose. For this same duration, male subjects participating in the study should avoid passing the semen to female partners during sexual intercourse.

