- 11. Subjects with active tuberculosis (TB). Subjects with evidence of latent TB or a history of TB must have completed treatment or have initiated treatment for at least 1 month before the first dose of study drug (Day 1). If latent TB is suspected based on clinical or epidemiological grounds, it should be further investigated using the tuberculosis testing as appropriate following local practice or investigator judgment.
- 12. Subjects who have received a live vaccine within last 3 months or non-live vaccine within 4 weeks of the first administration of study drug. [Note: A need may arise for trial subjects to receive vaccine against COVID-19 while being a part of the study. All such decisions will be taken at the discretion of the Investigator in consultation with the CRO / Sponsor after due consideration to subjects' safety, national health policy of the respective country and overall need by the subject for such vaccine during the time of study participation].
- 13. Subjects with an active uncontrolled infection requiring systemic treatment at Screening or history of documented recurrent clinically significant infection within 6 months of study inclusion (e.g., 2 or more viral, bacterial or fungal infections requiring in-patient treatment).
- 14. Subjects with New York Heart Association (NYHA) class III or IV congestive heart failure or relevant arrhythmia or angina based on ECG with clinical judgment.
- 15. Subjects with known hypersensitivity to rituximab or its excipients, or to proteins of murine or other foreign origin.
- 16. History or presence of a medical condition or disease that in the Investigator's opinion would place the subject at an unacceptable risk for study participation.
- 17. Participation in any clinical study or having taken any investigational therapy during the 2-month period immediately preceding administration of the first dose of study drug.

- 18. Lactating or pregnant female.
- 19. Women of childbearing potential who do not consent to use highly effective methods of birth control (e.g., sterilisation, or other non-hormonal forms of contraception) during treatment and for at least 12 months after the last administration of study drug. True abstinence periodic abstinence (e.g., calendar ovulation, symptothermal, post ovulation methods) and withdrawal are not acceptable methods of contraception.
- 20. Subject has been previously randomised in this study.

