10.3 Appendix 3: Contraceptive Guidance and Collection of Pregnancy Information

Definitions

Woman of Childbearing Potential (WOCBP)

A woman is considered fertile following menarche and until becoming post-menopausal unless permanently sterile (see below).

Women in the following categories are not considered WOCBP:

- Premenarchal
- Premenopausal female with one of the following:
 - a. Documented hysterectomy
 - b. Documented bilateral salpingectomy
 - c. Documented bilateral oophorectomy

NOTE: Documentation can come from the site personnel's review of the subject's medical records, medical examination, or medical history interview.

- Post-menopausal female
 - A post-menopausal state is defined as no menses for 12 months without an alternative medical cause. A high FSH level in the post-menopausal range may be used to confirm a post-menopausal state in women not using hormonal contraception or hormonal replacement therapy (HRT). However, in the absence of 12 months of amenorrhea, a single FSH measurement is insufficient.
 - Females on HRT and whose menopausal status is in doubt will be required to use one of the non-oestrogen hormonal highly effective contraception methods if they wish to continue their HRT during the study. Otherwise, they must discontinue HRT to allow confirmation of post-menopausal status before study enrolment.

Contraception Guidance:

Male Subjects:

Male subjects with female partners of childbearing potential are eligible to participate if they agree to ONE of the following during the protocol-defined time frame in Section 5.1:

- Are abstinent from penile-vaginal intercourse as their usual and preferred lifestyle (abstinent on a long-term and persistent basis) and agree to remain abstinent.
- Agree to use a male condom plus partner use of a contraceptive method with a failure rate of <1% per year as described in the table below when having penile-vaginal intercourse with a WOCBP who is not currently pregnant.

In addition, male subjects must refrain from donating sperm for the duration of the study and for 12 months after the last dose of study drug.

Male subjects with a pregnant or breastfeeding partner must agree to remain abstinent from penilevaginal intercourse or use a male condom during each episode of penile penetration during the duration of the study and for 12 months after the last dose of study drug.

Female Subjects

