Female subjects of childbearing potential are eligible to participate if they agree to use a highly effective method of contraception consistently and correctly as described in the table below.

Highly Effective Contraceptive Methods That Are User Dependent¹

Failure rate of <1% per year when used consistently and correctly.

Combined (oestrogen- and progestin-containing) hormonal contraception associated with inhibition of ovulation²

- Oral
- Intravaginal
- Transdermal

Progestogen-only hormonal contraception associated with inhibition of ovulation

- Oral
- Injectable

Highly Effective Contraceptive Methods That Are User Independent¹

Implantable progestogen-only hormonal contraception associated with inhibition of ovulation²

- Intrauterine device (IUD)
- Intrauterine hormone-releasing system (IUS)
- Bilateral tubal occlusion

Vasectomized Partner

A vasectomized partner is a highly effective contraception method provided that the partner is the sole male sexual partner of the WOCBP and the absence of sperm has been confirmed. If not, an additional highly effective method of contraception should be used.

NOTES:

- 1 Typical use failure rates may differ from those when used consistently and correctly. Use should be consistent with local regulations regarding the use of contraceptive methods for subjects participating in clinical studies.
- 2 Hormonal contraception may be susceptible to interaction with the study intervention, which may reduce the efficacy of the contraceptive method. In this case, 2 highly effective methods of contraception should be utilized during the treatment period and for at least 12 months after the last dose of study intervention.

Pregnancy Testing

- Woman of childbearing potential should only be included after a confirmed menstrual period and a negative highly sensitive serum pregnancy test.
- Additional pregnancy testing should be performed at every dosing visit during the treatment period and at EOS/ET and whenever pregnancy is suspected or at the discretion of the Investigator.
- Pregnancy testing will be performed whenever a menstrual cycle is missed or when pregnancy is otherwise suspected.

Collection of Pregnancy Information:

Male subjects with partners who become pregnant

- The Investigator will attempt to collect pregnancy information on any male subject's female partner who becomes pregnant while the male subject is in this study. This applies only to male subjects who receive study drug.

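### Inclusion 12 gives as examples of non-childbearing status women whom Appendix 3 still treats as of childbearing potential, so a site could omit required contraception

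*Protocol*

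**What the plan says.** Inclusion 12, in the Synopsis and in Protocol Section 5.1, opens with a rule for all women: "If female subject, then subject should be non-pregnant, non-lactating". It then accepts either adequate contraception or "post-menopausal/non-childbearing status (e.g., women with cessation of menstruation for ≤ 2 years, peri-menopausal women with inconclusive menopausal evidences", judged on clinical assessment and medical history. The contraception duty follows: "Women of childbearing potential must practice effective birth control for the duration of the study" and for 12 months after the last dose. Exclusion 19 in Section 5.2 is the counterpart and bars "Women of childbearing potential who do not consent to use highly effective methods of birth control".

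Protocol Section 10.3 (Appendix 3) defines the term on which both criteria turn. "A woman is considered fertile following menarche and until becoming post-menopausal unless permanently sterile". "A post-menopausal state is defined as no menses for 12 months without an alternative medical cause". It adds that "in the absence of 12 months of amenorrhea, a single FSH measurement is insufficient". Its categories outside childbearing potential are premenarchal, documented surgical sterility and post-menopausal. Its own eligibility rule reads: "Female subjects of childbearing potential are eligible to participate if they agree to use a highly effective method of contraception".

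Neither Inclusion 12 nor Exclusion 19 refers to Section 10.3. The same examples also stand in Section 8.3.4 and Table 10-4, where they illustrate who may need an FSH test.

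**The concern.** Inclusion 12 offers non-childbearing status as the alternative to contraception, so its examples work in practice as an exemption. A woman whose periods stopped five months ago fits the first example. A peri-menopausal woman with inconclusive evidence fits the second. Section 10.3 treats both as still of childbearing potential.

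What is at stake is participant and fetal safety. The sponsor asks for contraception throughout the study and for 12 months afterwards, and Section 8.4.10 stops study drug if pregnancy is reported. A site that classifies from the eligibility criterion alone could leave such a woman without contraception during that time while believing that it had followed the protocol.

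**Working it through.** No arithmetic applies. The check sets the two texts side by side for a woman who is not permanently sterile.

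| Woman | Examples in Inclusion 12 | Section 10.3 | Result |
|---|---|---|---|
| Under 12 months of amenorrhoea | Non-childbearing | Childbearing potential | Conflict |
| 12 to 24 months, no other cause | Non-childbearing | Post-menopausal | Agree |
| Over 24 months, no other cause | Outside the first example | Post-menopausal | No conflict, since the list is only illustrative |
| Peri-menopausal, inconclusive, not on HRT | Non-childbearing | Childbearing potential | Conflict |
| On HRT, status in doubt | Non-childbearing by the second example | Contraception, or stop HRT and confirm status before enrolment | Covered by a separate rule |

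1. **Is the wording a conversion fault?** No. The two-year upper limit appears with the same sign in the Synopsis, Section 5.1 and Section 8.3.4. Table 10-4 prints a strict inequality. None of them gives a lower limit.

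2. **Is it a deliberate rule?** Probably not. The examples describe women of uncertain status, which suits the FSH entries in Section 8.3.4 and Table 10-4. The amendment history in Section 10.6 records the words being added to those entries under Amendment 2. This suggests, without proving, that they are misplaced in Inclusion 12. The first example even leaves out the clearest post-menopausal women, those beyond two years.

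3. **Does another contraception rule catch the misclassified woman?** Only if she takes HRT. The duties in Inclusion 12, Exclusion 19 and Section 10.3 are all limited to women of childbearing potential, which is the class that the examples blur.

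4. **Do the pregnancy provisions catch her?** In part. Every female subject must be non-pregnant at entry, and Exclusion 18 bars pregnant women. Section 10.3 requires a test when a cycle is missed or pregnancy is suspected. The visit lists for Days 8 to 22, Week 8, Weeks 12 to 36 and Week 52 state no restriction by class, nor do the schedule sentences of Section 8.3.4. The Screening and Baseline lists and footnote 9 of Table 1-1 do restrict testing to women of childbearing potential. These provisions reduce the chance of pregnancy at entry or of late detection. None of them requires contraception.

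**The case against.** The strongest reply is that the protocol already has a governing definition. Section 10.3 defines childbearing potential under its own heading, and Inclusion 12 and Exclusion 19 use that term in mandatory sentences. The disputed words are only examples in a parenthesis. The HRT rule shows that the protocol resolves doubt towards protection. A careful site would read the whole document and classify correctly.

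Much of this stands. It means that the protocol's intention is clear and that omission is possible rather than certain. It does not remove the conflict. The examples sit in the criterion that sites apply at enrolment, they are offered as the alternative to contraception, and nothing there sends the reader to Section 10.3.

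The reply also disposes of two stronger readings that a reader might infer:

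- **That contraception depends wholly on how the site classes the woman.** The HRT rule shows otherwise, because there doubt alone triggers contraception or confirmation of status.
- **That the FSH exemption from pregnancy testing in Sections 4.5 and 8.1.1 is a second contradiction.** It applies only when FSH demonstrates post-menopausal status, and Section 10.3 says that a single value cannot do so before 12 months of amenorrhoea. Read together, the texts are consistent. The exemption would merely be clearer with the condition stated.

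**Conclusion.** The conflict is real and should be corrected. It is confined to women with under 12 months of amenorrhoea and women of inconclusive status who are neither permanently sterile nor covered by the HRT rule. For them, a site that follows the Inclusion 12 examples could omit contraception that Section 10.3 requires. This rests on one assumption, that some sites classify from the eligibility criterion without consulting the appendix.

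The documents do not say how many women are affected. No efficacy endpoint, sample size or error rate is touched.

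A reader might want to measure the harm by counting infusions given before a woman reaches 12 months of amenorrhoea, or pregnancy tests missed under each text. The documents do not support either as a measure of impact. The first count assumes that amenorrhoea continues, so every woman in it later meets the post-menopausal definition; the women of most concern, whose periods return, are left out. The second shows only that the testing texts differ. Nor do the documents support the inference that pregnant women may be enrolled, because Inclusion 12 and Exclusion 18 both forbid it.

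**What to change.** 1. Delete the parenthesis of examples from Inclusion 12 in the Synopsis and in Section 5.1.
2. Cross-refer Inclusion 12 and Exclusion 19 to the definition in Section 10.3.
3. State that women with under 12 months of amenorrhoea, or of inconclusive status, are treated as of childbearing potential unless permanently sterile as defined in Section 10.3.

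The cost is amendment wording and a site letter. No visit or test is added. Some women, in a number the documents do not give, will need contraception and the pregnancy tests already scheduled. Section 10.3 also says that a woman of childbearing potential should be included only after a confirmed menstrual period. Once these women are classed correctly, that rule may make some of them ineligible, so the sponsor should say how it applies to them.

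Two optional clarifications, neither of which corrects an error: add the 12-month condition to the FSH exemption in Sections 4.5 and 8.1.1, and relabel the FSH entry in Section 8.3.4 and Table 10-4 as being for women whose menopausal status needs confirmation.
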